#### 6.2 Waiver or Alteration of Consent Process

*This applies for studies where informed consent will not be obtained, required information will not be disclosed, or the research involves deception.* NA

- Is a waiver or alteration of the consent process being requested for this study?
  - 🗆 Yes 🛛 🗹 No
- Is a waiver of the consent process being requested for parents for research involving children?

🗆 Yes 🛛 🗹 No

Is a waiver of the consent process for planned emergency research being requested?
 □ Yes □ No

# 6.3 International Research

• *Refer to the IRB's International Checklist and International Guidance to ensure that all relevant information described in those documents is included in this protocol. NA* 

#### 6.4 Confidentiality

- Describe the procedures in place to maintain confidentiality as follows:
  - Where and how data or specimens will be stored.
  - The hard copy of the information on the study record and the ICF will be stored in a locked cabinet in a locked room. The electronic version of the data will be stored in REDCap.
     Information that will be downloaded for analysis will be de-identified first. A copy of the ICF will be given to each subject and a copy retained in the subject's medical record. BMC, MGH & BWH will operate in a similar manner with all collected participant information being stored in a locked cabinet in a locked room. Transfer of interested parties contact information will occur via secure email or a secure Mass General Brigham maintained Dropbox.
    - Specifically, state where the study records, including both electronic and/or paper study documents including signed ICFs/assent forms, will be retained (stored) during the study (state the location for original document plus any copies that are made, e.g., if a copy of the ICF will be retained in the subject's medical record).
  - *How long the data or specimens will be stored.* Until the completion of the study and data analysis is complete.
  - Who will have access to the data or specimens?
     Only study-wide LIPP, BWH Research Facility, CTRC, HNRCA or MIRI laboratory staff

- Who is responsible for receipt or transmission of the data or specimens locally? LIPP study staff who are members of the MIRI ([name], [name] and study coordinator [name]) and BWH Research Facility. The minimum amount of information required for scheduling will be shared with laboratory or university staff that are involved in study visits. Data and specimens will be in a coded data set using a unique LIPP study code number. Physiological data will be sent via the BWH Research Facility, HNRCA or CTRC staff.
- How data and specimens will be transported.
   BWH Research Facility, HNRCA or MIRI LIPP study staff will transport specimens. Data and
  - specimens will be de-identified using a unique LIPP study code number.
- Whether data will be coded.
  - Yes we will use bar code identification
    - If so, specify if there is a key to the code that matches the subjects' study identification number with their name and who will have access to it.
       Any key to bar code information will be kept in the LIPP research study coordinator's office
- Whether videotapes and/or photographs of subjects will be capable of identifying the study subject. If so, indicate who will have access to (be able to view) these items and how long the videotapes or photographs will be retained for the study and what the plan is for their destruction. NA
- If identifiable screening data will be retained for the study, clarify why, and who will have access to it. Submit the screening log.

Screening log has been submitted. Access will be through the LIPP research study coordinator and/or PI.

It will be necessary to include HIPAA data on the screening log so that when approaching the potential subject postpartum one can refer to specific inclusion and exclusion criteria. Further, the screening log will be used as a contact source for the patient at the time of the postpartum visit and in order to contact via email or text message.

We have been very careful about ensuring privacy of study subjects whether screened or enrolled in our studies. The paper versions of the screening log will be maintained in a locked room in a locked file cabinet. The electronic version will be kept on a Tufts Medical Center server in a secure data file. Once the data is entered onto the REDCap database maintained by LIPP study staff at PBRC, the information will be de-identified and use only a secure unique study number.

- Clarify whether confidential genetic information will be collected from subjects. NA
  Data and specimens should be stored in a secure location only accessible by the research team.
  The PI must ensure that study documents are stored in a manner that protects the privacy of
  subjects and the confidentiality of study data.
- Indicate whether a Certificate of Confidentiality will be obtained. A Certificate of Confidentiality should be obtained for research involving collection of information that, if disclosed, could have adverse consequences for subjects or damage their financial standing, employability, insurability, or reputation. For more information, refer to NIH's Certificates of Confidentiality Kiosk. NA

#### 6.5 Provisions to Protect the Privacy Interests of Subjects

• Describe the steps that will be taken to protect subjects' privacy interests. "Privacy interest" refers to a person's desire to place limits on with whom they interact or to whom they provide personal information.

Personal information will only be available to LIPP, BWH Research Facility, MIRI, CTRC and HNRCA study staff. All other information will be de-identified for example for statistical analysis or DSMB review.

# PROTOCOL TITLE: Lifestyle Intervention in Preparation for Pregnancy (LIPP) VERSION DATE: March 31st, 2023

• Describe the steps that will be taken to make the subjects feel at ease with the research situation in terms of the questions being asked and the procedures being performed. "At ease" does not refer to physical discomfort, but the sense of intrusiveness a subject may or may not experience in response to questions, examinations, and procedures.

The consent form will describe the study procedures in detail. The study protocol will be explained to the subjects as well. At the time of the visit, the LIPP study staff (PI when available and study coordinator) in addition to the CTRC, HNRCA or BWH Research Facility staff will be present to answer any ongoing questions. For those subjects randomized to the intervention group, HNRCA or BWH Research Facility staff will be present during the visit as well as the training sessions. Hence, there will be continuity of staff with all subjects in the LIPP study.

• Under what circumstances will the research team access sources of information about the subjects. The only time the LIPP research team will access sources of information about potential subjects is when the postpartum delivery records are screened for subject eligibility and the outcome pregnancy and delivery.

# 6.6 Provisions to Monitor the Study to Ensure the Safety of Subjects

- Describe the plan to periodically evaluate the data regarding both harms and benefits to assess subject safety as follows: We will continue to have a DSMB to evaluate subject benefit and harm.
  - Study data, including safety data, untoward events, and efficacy data, will be reviewed on a regular basis.

Please refer to the DSMB charter.

- Who will review the data? The DSMB this will include representatives from Case Western Reserve in Cleveland, TMC in Boston and PBRC in Baton Rouge. This has been made available to the IRB
- How the safety information will be obtained and documented (e.g., case report forms, by telephone calls with participants, printouts of laboratory results, etc.).
   Per the format laid out in the DSMB which was in place in Cleveland.
- The frequency of data collection, including when safety data collection starts.
- Safety collection starts when the first subject is enrolled into the study, in particular for the intervention group starting training.
- The frequency or periodicity of review of cumulative data. This will depend on how there is progression of recruitment. In Cleveland we had a DSMB approximately twice in the first year of the grant. We will have a minimal of 1 DSMB meeting per year.
- The statistical tests for analyzing the safety data to determine whether harm is occurring. The LIPP study statistician who will be located at Pennington Biomedical in Baton Rouge will determine this.
- Any conditions that trigger an immediate suspension of the research or other action for the research.

Any severe adverse reaction will trigger a review and determination if this was related to the research protocol.

- The plan might include establishing a data monitoring committee which addresses all the above.
- Describe the entity responsible for monitoring the data, and their respective roles (e.g., the investigators, the research sponsor, a coordinating or statistical center, an independent medical monitor, a Data and Safety Monitoring Board (DSMB) /Data Monitoring Committee (DMC), and/or some other entity, and the timeframe for reporting events to this entity.
  - Submit a copy of the DSMB/DMC Charter if the study is monitored by a DSMB/DMC. We have submitted the DSMB Charter for the LIPP study in Cleveland as well as the two DSMB reports (both open and closed) to the Tufts Medical Center IRB.

PROTOCOL TITLE: Lifestyle Intervention in Preparation for Pregnancy (LIPP) VERSION DATE: March 31st, 2023

### 6.7 Compensation for Research-Related Injury

Does the research involve greater than minimal risk to subjects? (Alternatively, if minimal risk, is there potential risk of research-related injury?):

🗹 Yes 🛛 🗆 No

If Yes, describe the available compensation in the event of research related injury including:

- What this compensation will be (e.g. free medical care, payment for treatment, compensation for lost wages, dependent care, etc.). There is the potential for risk to the subjects in the intervention group, sprains and fatigue after exercise. These have not been of any severe degree to affect study participation based on the first year of experience in Cleveland. There will be no compensation for any injury or loss of employment.
- Who will provide this compensation (e.g. sponsor, institution, etc.)? NA
- What will count as a qualified harm (e.g., physical, psychological, economic, social, or other injury)? Qualified harm will be determined by a serious adverse event related to the study protocol as determined by the DSMB
- Whether only injuries "related" to study, participation will be covered. If yes, clarify how it will be determined what injuries are considered related, and who will decide this. NA
- Will the study distinguish between injury (short-term, resolvable) and impairment (often longer-term, potentially manageable, but not resolvable) and if so, why. NA
- The process subjects must follow to obtain compensation. If no funds are set aside for researchrelated injury and subjects and/or their insurance will have to pay for the treatment of such injuries, include a statement such as: "No funds have been set aside for research-related injury. You or your insurance carrier will be required to pay for medical care associated with your research-related injury."

This has been similar to the language in all of our previous consent forms.

"No funds have been set aside for research-related injury. You or your insurance carrier will be required to pay for medical care associated with your research-related injury."

#### **6.8** Economic Burden to Subjects

Does the research involve any costs to subjects?

🗆 Yes 🛛 🗹 No

#### **6.10 Vulnerable Populations**

*If the research involves individuals who are vulnerable to coercion or undue influence, describe the rationale for their inclusion and the additional safeguards included to protect their rights and welfare.* Will pregnant women be enrolled?

# 🗹 Yes 🛛 No

If Yes, describe the following:

• Any preclinical studies, including studies on pregnant animals, and clinical studies, including studies on non-pregnant women, that have been conducted that provide data for assessing potential risks to pregnant women and fetuses.

The preliminary data that was obtained in Cleveland was data that included the number of women who might be eligible based on inclusion and exclusion criteria. The other preliminary data was the review of the average time to the second pregnancy. None of these information provided data related to risk to subjects relative to intervention.

• Whether the risk to the fetus is caused solely by interventions or procedures that hold out the prospect of direct benefit for the woman or the fetus or if there is no prospect of benefit to the fetus, the risk to the fetus is NOT greater than Minimal Risk, and the purpose of the research is the development of important biomedical knowledge which cannot be obtained by any other means.

There is no risk to the fetus from participation in the study. The ACOG recommends that pregnant women partake in physical activity during pregnancy for 30 min at least 5 days a week. Our study protocol recommends that all subjects follow ACOG guidelines for diet and physical activity and gain weight according to IOM recommendations from 2009.

• The biomedical knowledge that is expected to result from this research for this population. Importance of the Knowledge Gained

The importance of the knowledge to be gained by this proposal is the ability to determine if Lifestyle Interventions in Preparation for Pregnancy can achieve concrete (real) results in the efforts to stem the epidemic of obesity in women and their offspring. This study will also provide information as to the mechanisms of why lifestyle intervention before rather than only during pregnancy results in improved outcomes. Although the concept of pre-pregnancy lifestyle intervention has been recognized previously as potentially worthwhile, there have been few if any studies employing such a study design, because of the perceived difficulty in recruiting women prior to pregnancy. Based on our history of conducting research studies in women before during and after pregnancy, a study design of recruiting obese women immediately after pregnancy and incorporating the community into the lifestyle interventions, we believe that this approach will have applicability in many other populations.

The risks to subjects are minimal. They are the standard of care we should provide to all our obese patients considering future pregnancy. Our ability to provide more than a minimal amount of information is hampered by the lack of resources particularly for women seeking care without considerable personal resources. If successful, as proof of principle, we believe this protocol can serve as a paradigm for a wider initiation of lifestyle interventions before pregnancy.

- *How any risk of this research is the least possible for achieving the objectives of the research?* Risk will be minimized by having trained lifestyle intervention staff supervise physical activity and nutritionist the healthy eating for the Intervention group. The usual care group will receive benefit from having specific goals provided by our research team but not specific follow-up per the study protocol.
- How mothers providing consent are informed of the reasonably foreseeable impact of the research on the fetus or neonate.

Mothers are informed by the PI of the study and potential benefits of healthy eating and exercise before pregnancy. They will also be informed of the foreseeable impact of the research on their fetus/neonate.

- Specify that no inducements, monetary or otherwise, will be offered to terminate a pregnancy and that in the case of a fetus, the fetus is not the subject of a planned abortion. NA
- Specify that individuals engaged in the research will have no part in any decisions as to the timing, method, or procedures used to terminate a pregnancy or in determining the viability of a neonate. NA

Will the research involve neonates of uncertain viability or non-viable neonates?

🗆 Yes 🛛 🗹 No

# Will subjects who are not yet adults (neonates, children, teenagers) be enrolled? *Neonates will be included in the study as an outcome measure.*

- a. A Check to confirm that you will follow "SOP: Legally Authorized Representatives, Children, and Guardians (HRP-013)" to determine whether a prospective subject has or has not attained the legal age for consent to treatments or procedures involved in the research under the applicable law of the jurisdiction in which the research will be conducted. (e.g., individuals under the age of 18 years). If this SOP will not be followed, describe how this (attainment of legal age for consent or not) will be determined:
- b. *How permission to participate in the study will be obtained from the parents or legal guardians:* See Informed Consent section above. Permission will be obtained from parents or legal guardians as described in that section.

PROTOCOL TITLE: Lifestyle Intervention in Preparation for Pregnancy (LIPP) VERSION DATE: March 31st, 2023

- c. The assent process of children as follows:
  - i. *Any waiting period available between informing the prospective subject and obtaining the assent:* N/A
  - ii. Any process to ensure ongoing assent: N/A
  - iii. Research team members involved in the assent process: N/A
  - iv. How long children will have to consider study participation: N/A
  - v. Steps that will be taken to minimize the possibility of coercion or undue influence: N/A
  - vi. Steps that will be taken to ensure the subjects' understanding: N/A
  - vii. *If assent will not be obtained from children, specify why:* All children enrolled will be infants without the capacity to provide informed assent.
  - viii. If children reach 18 years of age while in the study describe the following:
    - 1. The plan to obtain written informed consent from the subject at age 18 years: N/A
      - 2. Who will be responsible for managing the plan: N/A
      - 3. Where the consent discussion will take place: N/A
      - 4. What will happen if the subject cannot be located to provide consent at age 18 years: N/A

Will minors under the age of 18 who are:

- i) married, widowed, divorced; or
- ii) the parent of a child; or
- iii) a member of any of the armed forces; or
- iv) pregnant or believes herself to be pregnant; or
- v) living separate and apart from his/her parent or legal guardian, and is managing his/her own financial affairs

Be approached for study participation for either themselves or their child?

🗆 Yes 🛛 🗹 No

Will wards of the state and/or children at risk of becoming wards of the state be enrolled (this includes foster children or any child that is in state custody)?

#### 🗆 Yes 🛛 🗹 No

Will cognitively impaired adults (adults with impaired-decision making capacity) or adults who may lose the capacity to consent be enrolled?

# 🗆 Yes 🛛 🗹 No

Will prisoners be enrolled?

🗆 Yes 🛛 🗹 No

Will students and/or employees be enrolled in this research?

🗹 Yes 🛛 No

If Yes, describe the following:

- Justification for specifically recruiting and enrolling students and/or employees into the study. Women who are overweight or obese delivering babies at TMC will be given the opportunity to enroll like any other subject who meets inclusion criteria.
- *How potential coercion will be eliminated.* By strictly following inclusion and exclusion guidelines.
- Recruitment methods to be applied specifically to students or employees. If the same recruitment methods previously described in the protocol will be used, then state that. N/A, The same criteria used for recruitment will apply to all potential subjects. No specific recruitment aimed at employees

PROTOCOL TITLE: Lifestyle Intervention in Preparation for Pregnancy (LIPP) VERSION DATE: March 31st, 2023

- *Additional safeguards included to protect the rights and welfare of students and employees.* No other than has already been described.
- Protections to ensure that a subject's participation or early withdrawal from the study will not affect his/her status as a student or employee. Per the statements in the approved subject consent form
- Submit a letter from the appropriate institutional official (e.g., Department Chair, Vice-President) who oversees the students and/or employees attesting to the fact that the employee or student's participation in the research is acceptable and that coercion has been minimized.

### 7 Adverse Event Monitoring

#### 7.1 Definitions

• Define adverse events (AEs), serious adverse events (SAEs), and unanticipated problems for your study.

Please refer to the DSMB definitions

During the course of the LIPP study, all adverse events (AEs) and serious adverse events (SAEs) will be monitored, documented, and if causal reported to BWH, TMC and the PBRC and the Data Safety Monitoring Board (DSMB). The Chair of the DSMB will be located at the PBRC. Every attempt will be made to follow a subject who has had negative reaction to any study intervention or procedure.

#### **General Reporting Guidelines**

#### Adverse Events (AEs)

An Adverse Event (AE) is any unfavorable medical occurrence, which may include abnormal signs (for example, abnormal physical exam or laboratory finding), symptoms, or disease, temporally associated with, but not necessarily considered related to, the subject's participation in the LIPP research study. These events are usually of a non-serious nature and are not reportable in accordance with the Institutional Review Board guidelines of the respective hospitals/ Universities for "Reportable Events," as they do not pose risk to study subjects.

Adverse events that take place during the course of the LIPP study will be classified under the Common Terminology Criteria for Adverse Events (CTCAE), a descriptive terminology used for Adverse Event (AE) reporting. AEs will be categorized as expected or unexpected in terms of their nature, severity, or frequency as outlined in the consent form. AEs will be graded using the CTCAE system and relatedness assessed by the PI and presented to the DSMB at DSMB meetings.

[figure not shown]
#### Serious Adverse Events (SAEs)

Serious Adverse Events (SAEs) or "Unanticipated Problems Involving Risk to Subjects or Others," are characterized as symptoms which are harmful to the subject and result in significant outcomes which are reportable to the respective IRBs and the study's DSMB.

[figure not shown]
Examples of serious adverse events are:

- Death
- Life threatening medical events that place a subject at immediate risk of death from the event as it occurred
- Results in impatient hospitalization or prolongation of existing hospitalization
- Results in persistent or significant disability or incapacity as a result of the study intervention
- Events that, based upon appropriate medical judgment, may jeopardize the subject's health and may require medical or surgical intervention to prevent one of the other outcomes listed in this definition.

The flow chart below provides an algorithm for determining whether an adverse event meets the definition of an "unanticipated problem involving risk to subjects or others."

PROTOCOL TITLE: Lifestyle Intervention in Preparation for Pregnancy (LIPP) VERSION DATE: March 31st, 2023

Adverse Events which follow the above figure, that meet the criteria of unexpected, fatal or lifethreatening, and related or possibly related to the research intervention must be reported to the IRB and the DSMB within 24 hours of learning of the event. If necessary, a subsequent follow-up report with the details of the event will be submitted as well. All other reportable adverse events will be submitted to the IRB within 10 working days of the investigator learning of the event. Reportable events will be submitted through the respective IRB's system.

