# PROTOCOL TITLE: Lifestyle Intervention in Preparation for Pregnancy (LIPP) VERSION DATE: March 31st, 2023

- When blood is drawn from a vein there will be some temporary discomfort and the minimal risk of local bruising, infection or blockage of the vein. We will take suitable precautions including trained staff who are certified to draw blood in volunteer subjects using an indwelling catheter, and minimal size needles to obtain the samples will help to minimize these risks.
- \* There are no risks to performing the Indirect Calorimetry to estimate resting energy expenditure.
- \* The possible risks of the oral glucose tolerance test consist of occasional nausea and very rarely vomiting or lightheadedness.
- \* There are no known risks from using the Bod Pod method to measure body fat composition.
- \* For those randomized to the Lifestyle Intervention group, risks include possible injury such as muscle and joint sprains during the exercise sessions.
- While exercising or performing the VO2 max test, subjects might experience fatigue or shortness of breath. They might also feel like their heart is pounding very fast or very hard and experience dizziness, heart rhythm abnormalities, chest pain, or very rarely a heart attack or death. They could stumble and fall off the treadmill. If subjects have any of these experiences, they are instructed to tell the research team. Also, when the mask is on their face, this might feel uncomfortable.
- \* There are no known additional risks from performing the metabolic tests.
- \* There is the potential risk of loss of confidentiality of the results of metabolic testing. We make every effort to minimize these risks by keeping paper records in a locked cabinet in a locked office. Any information held in electronic form will be kept on a secure computer in the research area of the hospital. Information containing personal data, for example birthday will be de-identified using a research hospital code number.

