# AE and SAE Assessment Guidelines Specific to the LIPP Study

*Key Criteria:* to determine if the event is unexpected, related to participation in the research study and involves risk to human subjects or others.

If an adverse event meets the criterion of unexpected, related or possibly related, and poses risk of harm to other subjects, the study coordinator will notify one of the Multiple Principal Investigators, [name] or [name], within 24- hours who will then inform the DSMB Chair and the Tufts Health Sciences IRB; the reviewing IRB of record.

To evaluate AEs and SAEs, a licensed medical professional will apply the following assessment criteria:

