#### **Event Expectedness**

#### Unexpected Medical Events:

These are the medical events that are not described in the current IRB-approved protocol or informed consent, taking into account the characteristics of the participant population being studied (e.g. pregnant population). *Expected medical events*\*:

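### Read literally, both 24-hour safety-reporting routes exclude a related fatal or life-threatening exercise event because the protocol already describes heart attack and death as risks

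*Combined protocol and SAP*

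**What the plan says.** Four parts of the protocol bear on this.

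- **The 24-hour rule (section 7.1, Serious Adverse Events).** It covers events that are "unexpected, fatal or lifethreatening, and related or possibly related to the research intervention must be reported to the IRB and the DSMB"; the limit is 24 hours from when the study learns of them. The next timing rule is: "All other reportable adverse events will be submitted to the IRB within 10 working days".
- **The internal alert (section 7.1, AE and SAE Assessment Guidelines Specific to the LIPP Study).** The coordinator has 24 hours to tell a principal investigator, who then informs the DSMB chair and the IRB. The trigger is: "If an adverse event meets the criterion of unexpected, related or possibly related, and poses risk of harm to other subjects".
- **The definition of unexpected (section 7.1, Event Expectedness).** "These are the medical events that are not described in the current IRB-approved protocol or informed consent", with a further clause that allows for the characteristics of the study population.
- **The named exercise risks.** Section 2.2 warns that a woman exercising or doing the VO2max test may "experience dizziness, heart rhythm abnormalities, chest pain, or very rarely a heart attack or death". The Serious Adverse Event table in 7.1 has four entries: heart attack and death, each for VO2max testing and for structured exercise.

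On oversight, section 6.6 says "We will have a minimal of 1 DSMB meeting per year". Section 7.1 also makes serious adverse events reportable to the IRBs and the DSMB, and has causal events reported to the sites and the DSMB. Neither statement carries a time limit.

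**The concern.** Expectedness is a sensible filter for minor events. Here it also governs the gravest ones. A protocol that names a fatal risk, as it should for honest consent, thereby makes that event expected under its own definition and takes it out of its own fastest reporting rule. The events affected are the most serious ones the protocol attaches to the intervention and its testing.

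At stake is how quickly the IRB and DSMB learn of a related exercise death or life-threatening event while other women are still training and being tested. This is a question of notification time. It does not bear on the efficacy analysis or on the exercise programme itself.

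**Working it through.** No figure in the plan needs reproducing. The check is to pass one event through each rule. Take a fatal cardiac event on the treadmill, or during a supervised session, that the assessor judges related.

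**Step 1: is it unexpected?** The Event Expectedness definition asks whether the event is described in the protocol or the consent. I read description in either document as enough. Section 2.2 describes heart attack and death for both settings, and the Serious Adverse Event table repeats them. Literal answer: not unexpected.

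**Step 2: apply the routes.**

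| Route (section 7.1) | Conditions, all required | Result for this event |
|---|---|---|
| 24 hours to IRB and DSMB | unexpected; fatal or life-threatening; related or possibly related | fails the first, meets the other two |
| 24 hours, coordinator to principal investigator, then DSMB chair and IRB | unexpected; related or possibly related; risk of harm to other subjects | fails the first, whatever is decided on the third |
| 10 working days to IRB | other reportable adverse events | applies; the DSMB is not named in this sentence |
| Report to DSMB as a serious or causal event | serious, or judged causal | applies; no time limit stated |

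**Step 3: look for another clock elsewhere in the document.** Section 7.2 assigns deaths and life-threatening events to the principal investigator but gives no timeframe. It points back to the mechanisms in 7.1 and on to the DSMB charter. Section 7.3 refers to the IRB's policy on new information, which is not reproduced. Section 6.6 says a severe adverse reaction leads to a review of whether it was study-related, again without a deadline.

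**Step 4: the change in deadline.** For the IRB, the limit moves from 24 hours to 10 working days. With a five-day week and no holidays, that is 10 / 5 = 2 weeks, or 14 calendar days. For the DSMB, it moves from 24 hours to none stated.

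**Step 5: set the competing wording alongside.** Three places in 7.1 could reverse Step 1:

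- The general Adverse Events text judges expectedness by nature, severity or frequency against the consent form.
- The Event Expectedness definition has its population clause.
- The bulleted list of expected events covers pregnancy, fasting, hypoglycaemia, blood draws and the glucose drink. It names neither heart attack nor the death of a participant.

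The same event is therefore expected under the described-or-not test and arguably unexpected under these three. The document does not say which one governs.

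**The case against.** The best reply is that no sentence classes an exercise death as expected. The status is inferred from a definition, while the explicit list of expected events leaves it out. The participants are aged 18 to 40 without clinical signs of cardiovascular disease (section 4.1), and section 2.2 describes screening for EKG abnormalities. Under the population clause, an assessor could fairly call a cardiac death in such women unexpected, or say that even one exceeds the stated rarity. The consent form, flow chart and DSMB charter are not available, and any of them might settle the matter. Much of this stands. It rules out saying that the 24-hour rule can never reach these events.

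It does not remove the problem. Section 2.2 already states the nature, severity and rarity of these events, so an appeal to severity or frequency is discretionary. The list of expected events does not define what is unexpected; the definition above it does. The flow chart is introduced as a way to identify unanticipated problems, and the 24-hour sentence applies its own expectedness condition to events that have come through that chart. On the visible wording, the chart does not waive the condition.

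Two stronger readings are tempting. One is that such deaths would go unreported. They would not: section 7.1 keeps them reportable to the IRB and the DSMB. The other is that the DSMB might wait about a year. One meeting a year is a stated minimum, not the reporting interval, and the separate duty to report to the DSMB does not depend on a meeting.

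**Conclusion.** The concern holds as a conflict within the protocol. On the literal definition, a related fatal or life-threatening exercise event misses both 24-hour routes; on other wording in the same section, it may qualify. A deadline for the gravest named risk should not turn on which sentence an assessor applies.

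The size is the loss of the 24-hour clock: to 10 working days for the IRB, and to no stated limit for the DSMB. This rests on three assumptions:

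- description in the protocol alone is enough to make an event expected;
- the event is judged related or possibly related;
- the unseen flow chart and charter set no other deadline.

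A reader might try to scale the point by counting all exercise sessions and maximal tests in the trial. The documents do not support that as a measure of harm. They give no event rate; recruitment has closed at Pennington and Massachusetts General Hospital (section 4.4.2); and 40 to 50% dropout is expected (section 8.3). The case for changing the rule is that the gap concerns death and the remedy is cheap, not that many events are likely.

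**What to change.** In section 7.1, remove unexpected as a condition in both 24-hour routes for fatal or life-threatening events that are related or possibly related. These events would then go to the IRB and DSMB within the existing 24 hours, whether or not the protocol or consent describes them. Keep the relatedness criterion, and keep the expected/unexpected split for all other events.

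Reconcile the risk description in 2.2 with the 7.1 text on Adverse Events, Serious Adverse Events, the study-specific assessment guidelines, the expectedness definition and list, and the Serious Adverse Event table. One test of expectedness should remain. Check the flow chart against it and align the DSMB charter.

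The cost is a wording amendment to the protocol and charter, with IRB approval and a note to site staff. The downside is a few more expedited reports, which should be very rare given that the protocol itself describes heart attack and death in those terms. Eligibility, the exercise programme and the analysis are untouched.
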